5.2.2 Serious Adverse Events (Immediately Reportable to the Sponsor)

A serious adverse event is any adverse event that meets any of the following criteria:

- Is fatal (i.e., the adverse event actually causes or leads to death)
- Is life threatening (i.e., the adverse event, in the view of the investigator, places the participant at immediate risk of death)
 - This does not include any adverse event that had it occurred in a more severe form or was allowed to continue might have caused death
- Requires or prolongs inpatient hospitalization (see Section [5.3.5.12](#))
- Results in persistent or significant disability/incapacity (i.e., the adverse event results in substantial disruption of the participant's ability to conduct normal life functions)
- Is a congenital anomaly/birth defect in a neonate/infant born to a mother exposed to study drug
- Is a significant medical event in the investigator's judgment (e.g., may jeopardize the participant or may require medical/surgical intervention to prevent one of the outcomes listed above)

The terms "severe" and "serious" are not synonymous. Severity refers to the intensity of an adverse event (e.g., rated as mild, moderate, or severe; the event itself may be of relatively minor medical significance such as severe headache without any further findings).

Severity and seriousness need to be independently assessed for each adverse event recorded on the eCRF.

Serious adverse events are required to be reported by the investigator to the Sponsor immediately (i.e., no more than 24 hours after learning of the event; see Section [5.4.2](#) for reporting instructions).

5.2.3 Adverse Events of Special Interest (Immediately Reportable to the Sponsor)

Adverse events of special interest are required to be reported by the investigator to the Sponsor immediately (i.e., no more than 24 hours after learning of the event; see Section 5.4.2 for reporting instructions). Adverse events of special interest for this study include the following:

- Cases of potential drug-induced liver injury that include an elevated ALT or AST in combination with either an elevated bilirubin or clinical jaundice, without evidence of another liver or biliary disorder as defined by Hay's Law (see Section 5.3.5.8)
- Suspected transmission of an infectious agent by the study drug, as defined below:
 - Any organism, virus, or infectious particle (e.g., prion protein transmitting transmissible spongiform encephalopathy), pathogenic or non-pathogenic, is considered an infectious agent. A transmission of an infectious agent may be suspected from clinical symptoms or laboratory findings that indicate an infection in a participant exposed to a medicinal product. This term applies only when a contamination of the study drug is suspected

5.2.4 Selected Adverse Events

Data on associated symptoms and safety MRI scans will be collected for the following selected adverse events:

- ARIA-E: ARIAs suggestive of vasogenic edema and sulcal effusions
- ARIA-H: ARIAs suggestive of microhemorrhages and/or hemosiderin deposits

Please refer also to Section 5.3.5.1 for further details how to report ARIA events.

5.3 METHODS AND TIMING FOR CAPTURING AND ASSESSING SAFETY PARAMETERS

The investigator is responsible for ensuring that all adverse events (see Section 5.2.1 for definition) are recorded on the adverse event eCRF and reported to the Sponsor in accordance with instructions provided in this section and in Sections 5.4–5.6. The investigator is also responsible for reporting medical device complaints (see Section 5.4.4)

For each adverse event recorded on the adverse event eCRF, the investigator will make an assessment of seriousness (see Section 5.2.2 for seriousness criteria), severity (see Section 5.3.3), and causality (see Section 5.3.4).

5.3.1 Adverse Event Reporting Period

Investigators will seek information on adverse events at each participant contact. All adverse events, whether reported by the participant/caregiver or noted by study personnel, will be recorded in the participant's medical record and on the adverse event eCRF.

After informed consent has been obtained but prior to the first administration of study drug in this study, only serious adverse events caused by a protocol-mandated intervention (e.g., invasive procedures, discontinuation of medications) should be reported (see Section 5.4.2 for instructions for reporting serious adverse events).

After the first dose of study drug in this study, all adverse events will be reported until the participant's last visit (including long-term follow-up visit).

Instructions for reporting adverse events that occur after the adverse event reporting period are provided in Section 5.6.

5.3.2 Eliciting Adverse Event Information

A consistent methodology of non-directive questioning should be adopted for eliciting adverse event information at all participant evaluation timepoints. Examples of non-directive questions include the following:

- "How have you felt since your last clinic visit?"
- "Have you had any new or changed health problems since you were last here?"

5.3.3 Assessment of Severity of Adverse Events

Table 2 provides guidance for assessing adverse event severity.

Table 2 Adverse Event Severity Grading Scale

Severity	Description
Mild	Discomfort noticed, but no disruption of normal daily activity
Moderate	Discomfort sufficient to reduce or affect normal daily activity
Severe	Incapacitating with inability to work or to perform normal daily activity

Note: Regardless of severity, some events may also meet seriousness criteria. Refer to definition of a serious adverse event (see Section 5.2.2).

5.3.4 Assessment of Causality of Adverse Events

Investigators should use their knowledge of the participant, the circumstances surrounding the event, and an evaluation of any potential alternative causes to determine whether an adverse event is considered to be related to the study drug, indicating "yes" or "no" accordingly. The following guidance should be taken into consideration:

- Temporal relationship of event onset to the initiation of study drug
- Course of the event, with special consideration of the effects of dose reduction, discontinuation of study drug, or reintroduction of study drug (as applicable)
- Known association of the event with the study drug or with similar treatments
- Known association of the event with the disease under study

- Presence of risk factors in the participant or use of concomitant medications known to increase the occurrence of the event
- Presence of non-treatment-related factors that are known to be associated with the occurrence of the event

5.3.5 Procedures for Recording Adverse Events

Investigators should use correct medical terminology/concepts when recording adverse events on the adverse event eCRF. Avoid colloquialisms and abbreviations.

Only one adverse event term should be recorded in the event field on the adverse event eCRF.

5.3.5.1 Amyloid-related Imaging Abnormality Findings

Not every ARIA finding in MRI qualifies as an adverse event. An ARIA finding must be reported as an adverse event if it meets any of the following criteria:

- ARIA-E which is symptomatic (i.e., accompanied by CNS symptoms), and/or
- ARIA that results in a change in study treatment (e.g., dosage modification, treatment interruption, or treatment discontinuation), and/or
- Is otherwise clinically significant in the investigator's judgment

Any accompanying symptoms should also be captured as separate adverse events.

It is the investigator's responsibility to review all ARIA findings.

Observations of the same clinically significant ARIA finding should only be recorded once on the adverse event eCRF (see Section 5.3.5.5 for details on recording persistent adverse events).

5.3.5.2 Injection Reactions

Injection reactions (local and systemic) are defined as adverse events that occur during or within 24 hours after study drug administration and that are judged to be related to the study drug injection.

For local reactions, the diagnosis of ISR should be captured on the adverse event eCRF and associated signs and symptoms (e.g., erythema at injection site) should be recorded on the dedicated injection-site reaction eCRF.

Systemic reactions should be recorded as a single diagnosis on the adverse event eCRF (e.g., anaphylactic reaction). If possible, avoid ambiguous terms such as "systemic reaction."

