2. OBJECTIVES AND ENDPOINTS

The main objective of this study (*Part 1 and Part 2*) is to continue to collect long-term safety and tolerability data in participants with AD treated with gantenerumab. Specific objectives and corresponding endpoints for the study are outlined in [Table 1](#).

Table 1 Objectives and Corresponding Endpoints

Safety Objective	Corresponding Endpoints

 • To evaluate the long-term safety and tolerability of continued treatment with SC gantenerumab at target dose in participants with AD who received gantenerumab in OLEs of Studies WN25203 or WN28745 	
 • Nature, frequency, severity, and timing of AEs and SAEs • Physical examinations (including neurological systems), vital signs, blood tests, ECGs, and C-SSRS • Nature, frequency, severity, and timing of MRI findings: ARIA-E and ARIA-H • Nature, frequency, severity, and timing of injection-site reactions • Immunogenicity of long-term treatment with gantenerumab through the measurements of ADAs • Incidence of treatment discontinuations for AEs • Incidence of AEs of special interest
Exploratory Efficacy Objective	Corresponding Endpoint

 • To assess the long-term clinical effect in participants with AD 	
 • MMSE total score will be used to assess AD progression

Table 1 Objectives and Corresponding Endpoints (cont.)

Exploratory Pharmacodynamic Biomarker Objective	Corresponding Endpoints

• To evaluate the long-term effect of gantenerumab in participants with AD	
• MRI-derived measurements over time, such as volumetric changes in whole brain, ventricles, hippocampus, or other structures, in all participants• Plasma pharmacodynamic biomarkers over time

AD = Alzheimer's disease; ADA = anti-drug antibodies; AE = adverse event; ARIA-E = amyloid-related imaging abnormalities–edema/effusion; ARIA-H = amyloid-related imaging abnormalities–hemosiderin deposition; C-SSRS = Columbia-Suicide Severity Rating Scale; ECG = electrocardiogram; MMSE = Mini Mental State Examination; MRI = magnetic resonance imaging; OLE = open-label extension; SAE = serious adverse event; SC = subcutaneous

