5. ASSESSMENT OF SAFETY

5.1 SAFETY PLAN

Gantenerumab is not yet approved, and clinical development is ongoing. The safety plan for participants in this study is based on clinical experience with gantenerumab in completed and ongoing studies. The identified risks for gantenerumab are outlined below. Please refer to the gantenerumab IB for a complete summary of safety information.

Several measures will be taken to ensure the safety of participants in this study. Eligibility criteria have been designed to exclude participants at higher risk for imaging related abnormalities. Participants will undergo safety monitoring during the study, including assessment of the nature, frequency, and severity of adverse events. In addition, guidelines for managing adverse events, including criteria for dosage modification and treatment interruption or discontinuation, are provided below.

Participants should be observed for a minimum one-hour post IMP administration. Rescue medications to treat anaphylactic and anaphylactoid reactions must be available at the site or at the dosing location for MN visits. Participants and their study partners will be alerted to watch for signs of anaphylactic and anaphylactoid reactions and to contact the study center as soon as possible if any such signs are noted (refer to the pharmacy manual).

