5.1.1.2 Injection-Site Reactions

Gantenerumab may cause a reaction when given as an SC injection. In studies with gantenerumab, the most common adverse events occurring more frequently with gantenerumab than with placebo were local ISRs, such as injection-site erythema. The majority of events were of mild intensity and resolved without treatment.

Detailed information on the characteristic signs and symptoms of ISRs (e.g., erythema, pruritus) will be recorded on the dedicated eCRF page.

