6.5 SAFETY ANALYSES

The safety analysis population will include all participants in the safety population who received at least one dose of study drug. The following safety outcome measures will be summarized using descriptive statistics:

- Incidence, nature, severity, and timing of adverse events
- Incidence, nature, severity, and timing of serious adverse events
- Changes from baseline of this study in vital signs, blood tests, ECGs, and C-SSRS
- Incidence, nature, severity, and timing of MRI safety findings: ARIA-E and ARIA-H
- Incidence, nature, severity, and timing of ISRs
- Number and proportion of ADA-positive and ADA-negative participants during both the treatment and follow-up periods
- Incidence of treatment discontinuations for adverse events
- Incidence of adverse events of special interest

Statistical methods, endpoint definitions and analyses of the safety endpoints will be described in the Statistical Analysis Plan.

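### The only ISR definition stops at 24 hours after dosing, so an ISR summary built on it can only understate incidence and cannot show later onset; summarise related injection-site AEs of any onset beside it

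*Combined protocol and SAP*

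**What the plan says.** Section 5.3.5.2 gives the definition: "Injection reactions (local and systemic) are defined as adverse events that occur during or within 24 hours after study drug administration". The same sentence joins a second condition, causality, to this time window. The two conditions are joint, and the parenthesis brings local reactions under the same window as systemic ones. The section then ties the ISR label to that class: "For local reactions, the diagnosis of ISR should be captured on the adverse event eCRF". It sends the associated signs and symptoms to a dedicated ISR form.

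The endpoint appears in Section 2, Table 1, as "Nature, frequency, severity, and timing of injection-site reactions", and in Section 6.5 as "Incidence, nature, severity, and timing of ISRs". Neither place defines an ISR or mentions a window.

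Section 5.1.1.2 describes ISRs without a time limit: "Detailed information on the characteristic signs and symptoms of ISRs (e.g., erythema, pruritus) will be recorded on the dedicated eCRF page". That is an instruction about a form, not a definition.

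Section 6.5 also says: "Statistical methods, endpoint definitions and analyses of the safety endpoints will be described in the Statistical Analysis Plan". The documents supplied contain no further ISR definition.

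**The concern.** ISRs are one of the two identified risks of the drug (Section 1.2.2; the other is ARIA), and the main objective of the study is long-term safety. A reaction at the injection site that the investigator attributes to the injection is what a reader expects the ISR line to count. Under Section 5.3.5.2, the clock alone can remove it from that line.

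Two features of the summary would then follow from the definition and not from the data. Incidence could be too low but never too high on this account. Onset measured from the dose could not exceed 24 hours, so the table could not answer whether late local reactions occur. In addition, Section 5.3.5.2 does not send the signs and symptoms of late reactions to the form designed for them.

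The cut-off is also hard to apply. Section 5.1 says "Participants should be observed for a minimum one-hour post IMP administration". Dosing visits are 4 weeks apart, and Section 5.3.2 asks for non-directive questioning about the time since the last visit. Whether a reaction began at 20 or at 30 hours will often rest on what a participant with Alzheimer's disease, or the caregiver, remembers weeks later.

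**Working it through.** **1. Apply the definition to single reactions.** All are local and judged related. I read the time condition as referring to onset, so a reaction that starts inside the window and lasts longer still counts.

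| Onset after dose | Time condition met | ISR diagnosis under 5.3.5.2 | ISR form directed by 5.3.5.2 | Recorded as an AE (5.3.1) |
|---|---|---|---|---|
| 6 h | yes | yes | yes | yes |
| 20 h, persisting past 24 h | yes | yes | yes | yes |
| 30 h | no | no | no | yes |

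**2. Trace the 30-hour reaction.** Section 5.3.1 has every AE reported from the first dose to the last visit. Section 5.3.4 attaches a yes/no causality judgement, and Section 5.3.5.3 asks for a diagnosis where one is known. The reaction is therefore in the database as a related AE and can be retrieved by its term. What it lacks is the ISR diagnosis and, as far as Section 5.3.5.2 directs, the ISR form.

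**3. Direction of the effect.** Let A be the number of participants with at least one related injection-site reaction of any onset, B the number with at least one starting within 24 hours, and N the number treated. Everyone in B is in A, so

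B/N ≤ A/N.

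The two are equal only if nobody has exclusively late reactions. The shortfall is (A − B)/N, the share of participants whose reactions are all late. For timing, onset minus dose time is at most 24 hours for every event counted. Dose number and study week carry no such bound.

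**4. Can the shortfall be sized?** The protocol's own ISR figures (Section 1.2.2, parent open-label extensions) reproduce:

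- WN25203: 56/154 = 36.4%
- WN28745: 90/225 = 40.0%
- Pooled: (56 + 90)/(154 + 225) = 146/379 = 38.5%

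They do not give the shortfall, for four reasons.

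- No section reports how ISR onset was distributed over time, so A − B has no source.
- The documents do not say which onset rule produced these figures. If it was also a 24-hour rule, 38.5% estimates B/N and not A/N.
- They cover everyone dosed in the extensions, whereas this study takes only those who completed without stopping drug (Section 4.1.1).
- A participant drops out of the count only if every reaction is late. Dosing every 4 weeks from Day 1 to Week 104 gives 104/4 + 1 = 27 scheduled doses in Part 1, and Weeks 108 to 208 give (208 − 108)/4 + 1 = 26 more. Someone who reacts repeatedly has many chances of one early reaction. Participant-level incidence may thus be less affected than event counts or the onset summary.

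The window covers 1 of the 28 days in a dosing interval (1/28 = 3.6%). That is a share of time and says nothing about the share of reactions.

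**The case against.** The strongest reply is that Section 5.3.5.2 is a recording rule, placed under the procedures for recording AEs, and that Section 6.5 reserves endpoint definitions for the SAP. This stands in part: a wider SAP definition would remove the problem, so a downward bias in the final report cannot be asserted as fact. But no such definition is in the documents supplied, and the recording rule decides which events carry the ISR label that the analysis would naturally use.

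Second, the stakes are modest. Section 1.2.2 reports no serious ISR in either parent study, with most mild and resolving untreated. The analysis is descriptive, and serious events and discontinuations for AEs are captured whatever the onset. A fixed attribution window is also a defensible convention. All of this stands, and it argues for a small repair.

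Third, Part 1 has enrolled and Part 2 continues the same participants. Rewriting the ISR definition now would mix two capture rules in one headline figure. This stands, and it is why the repair belongs in the analysis.

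Fourth, the recall argument also touches any 24-hour row that is kept, and each participant must have a caregiver in frequent contact. True, but a row covering all onset times does not depend on placing onset on one side of 24 hours. AEs are already elicited over the whole interval, so the recall period is not lengthened.

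A reader might also infer that Section 2 or Section 5.1.1.2 contradicts the window. They do not: the first only names the endpoint, and the second describes the reactions without defining them.

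**Conclusion.** The point holds as a matter of definition. The only ISR definition in the documents excludes related local reactions that start after 24 hours. A summary built on it can only understate ISR incidence, and it cannot show onset later than 24 hours after a dose. This rests on reading the time condition as onset and on the SAP adopting the Section 5.3.5.2 class unchanged.

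The size is unknown. It would be tempting to take the pooled 38.5%, assume a share of late-only reactors and quote a bias. The documents support neither the share nor the use of 38.5% as an all-onset rate, so no numeric range should be stated.

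Two other strong readings also fail. Late reactions do not disappear, because they remain in the AE data with a causality judgement. The timing endpoint is not truncated altogether, because timing by dose number or study week is intact. No sample size, error rate or hypothesis test is affected. This is an inexpensive improvement to a listed safety endpoint.

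**What to change.** **Analysis (Section 6.5 and the SAP).** Summarise all injection-site AEs judged related to the injection, whatever their time of onset, selected by AE term so that Part 1 and Part 2 are treated alike. State the list of terms. Say also which causality field is used, since Section 5.3.4 records relatedness to study drug and Section 5.3.5.2 speaks of the injection. Beside this, show the ISRs as defined in Section 5.3.5.2, in a row labelled as within 24 hours, for comparison with parent-study figures. The definition in Section 5.3.5.2 can stay as it is.

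**Data capture (remaining visits).** Instruct sites to complete the ISR eCRF and the onset date for related local reactions whatever their onset.

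**Cost.** One extra table row and a line of eCRF guidance. The all-onset rate may be slightly higher than the 24-hour rate. Late reactions already recorded in Part 1 will have less sign and symptom detail than later ones, so that detail should not be compared between the two parts. Where onset was established only by recall, the 24-hour row keeps its present uncertainty.

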5.3.5.3 Diagnosis vs. Signs and Symptoms

A diagnosis (if known) should be recorded on the adverse event eCRF rather than individual signs and symptoms (e.g., record only liver failure or hepatitis rather than

jaundice, asterixis, and elevated transaminases). However, if a constellation of signs and/or symptoms cannot be medically characterized as a single diagnosis or syndrome at the time of reporting, each individual event should be recorded on the adverse event eCRF. If a diagnosis is subsequently established, all previously reported adverse events based on signs and symptoms should be nullified and replaced by one adverse event report based on the single diagnosis, with a starting date that corresponds to the starting date of the first symptom of the eventual diagnosis.

5.3.5.4 Adverse Events That Are Secondary to Other Events

In general, adverse events that are secondary to other events (e.g., cascade events or clinical sequelae) should be identified by their primary cause, with the exception of severe or serious secondary events. A medically significant secondary adverse event that is separated in time from the initiating event should be recorded as an independent event on the adverse event eCRF. For example if:

- Vomiting results in mild dehydration with no additional treatment in a healthy adult, only vomiting should be reported on the eCRF
- Vomiting results in severe dehydration, both events should be reported separately on the eCRF
- A severe gastrointestinal hemorrhage leads to renal failure, both events should be reported separately on the eCRF
- Dizziness leads to a fall and consequent fracture, all three events should be reported separately on the eCRF
- Neutropenia is accompanied by an infection, both events should be reported separately on the eCRF

All adverse events should be recorded separately on the adverse event eCRF if it is unclear as to whether the events are associated.

